3.2.1.2 Relative day

Relative day will be calculated as the current date minus the date of first dose of study medication plus 1 for days on or after the day of first dose of study medication and prior to or on the day of last study medication dose (eg, the day of first dose will be Day 1). For days prior to the first dose of study medication (the day prior to first dose will be Day -1), relative day will be calculated as the current date minus the date of first dose of study medication. For days after the last dose of study medication, relative day will be calculated as the current date minus the date of last dose of study medication including a "+" to denote post-treatment days (eg, the day after the last dose will be Day +1). Relative day will not be calculated for partial or missing dates.

3.2.2 Study periods

This study consists of the following six periods: Baseline Period, Titration Period, Maintenance Period, Transition Period, Taper Period, and Safety Follow-Up Period. Additionally, for analysis purposes, the Treatment Period includes Titration and Maintenance Periods. Each period is defined in turn as follows for the classification by study period:

Baseline Period

This is defined as the period from the date of Visit 1 (entry to study) to 1 day prior to the date of first dose of study medication. In addition, pre-dose scheduled assessments which are performed on the date of first dose of study medication will be assigned to the Baseline Period. Any unscheduled assessments which are performed prior to the date of first dose of study medication will also be assigned to the Baseline Period.

Titration Period

This is defined as the period of time from the date of first dose of study medication to the last Titration Period visit date (Telephone Contact 3 [T3]) for subjects who complete the Titration Period, or from the date of first dose of study medication to the date of the Early Termination Visit (ETV) for subjects who prematurely discontinue prior to the last Titration Period visit date (T3). If a subject does not have a T3/ETV, then either the date of the last scheduled or unscheduled visit during the Titration Period or the date of last known dose of study medication, if this is after the last scheduled or unscheduled visit date during the Titration Period, will define the end date of the Titration Period.

Maintenance Period

This is defined as the period of time from the day after the end date of the Titration Period (T3) to the last Maintenance Period visit date (Visit 6 [Day 27]) for subjects who complete the Maintenance Period, or from the day after the end of the Titration Period (T3) to the date of the ETV for subjects who prematurely discontinue prior to the last Maintenance Period visit date last scheduled or unscheduled visit during the Maintenance Period or the date of last known dose of study medication, if this is after the last scheduled or unscheduled or Maintenance Period, will define the end date of the Maintenance Period.

Treatment Period

This is defined as the period of time from the date of first dose of study medication to the last Treatment Period visit date (Visit 6 [Day 27]) for subjects who complete the Treatment Period, or from the date of first dose of study medication to the date of the ETV for subjects who prematurely discontinue prior to the last Treatment Period visit date (Visit 6 [Day 27]). If a subject does not have a Visit 6 (Day 27)/ETV, then either the date of the last scheduled or unscheduled visit during the Treatment Period or the date of last known dose of study medication, if this is after the last scheduled or unscheduled visit date during the Treatment Period, will define the end date of the Treatment Period.

Transition Period

For those subjects who complete the Maintenance Period and plan to participate in the open-label extension study (EP0034), the Transition Period is defined as the date after the end of the Maintenance Period (Visit 6 [Day 27]) to the date of Transition Visit 2.

Taper Period

For those subjects who discontinue study medication or for those subjects who complete the Maintenance Period but choose not to enter EP0034, the Taper Period is defined as the date after the end of the Titration, Maintenance or Transition Period, whichever is later, to the date of the Taper Visit.

Safety Follow-Up Period

There will be a 30-day Safety Follow-Up Period for subjects not entering EP0034. The start of the Safety Follow-Up Period is defined as the day after the last dose of study medication in SP0967 and continues until the date of last telephone contact and/or 30 days after the last dose of study medication, whichever is later.

Mapping of assessments performed at Early Termination Visit

Efficacy and safety assessments at an ETV that correspond to a scheduled visit will be summarized at the scheduled visit corresponding to the ETV if the assessment was scheduled to Occur at that visit. Such assessments will also be considered for Last Visit.

3.2.4 Study visit labeling

Visits will be labeled in table summaries (according to the schedule outlined in Section 5.2 of the protocol) as follows:

"Baseline"

- "Visit X (Day X)" for scheduled visits during the Treatment Period
- "Transition Visit X" for scheduled visits during the Transition Period
- "Taper Period"
- "Safety Follow-up Period"
- "Last Visit" (see below in Section 3.2.5 for further information)

Listings will also include "Unscheduled Visit" as applicable.

3.2.5 Last visit

The Last Visit for all assessments in the study is the last non-missing assessment during the Treatment Period. All scheduled and unscheduled assessments within this time period will be considered. Last Visit will be determined separately for each study procedure where Last Visit is mentioned within this document.

3.2.6 Exposure duration

The overall duration of LCM exposure for each subject will be calculated as the date of the last dose of LCM minus the date of the first dose of LCM plus 1 day. Caps in treatment or days with unknown dosing will not be subtracted from the duration of exposure.

3.2.7 Age, age categorization, age at first diagnosis, epilepsy duration

For subjects who do not have a full date of birth reported based on region-specific regulations, age in years and months will be obtained from the Interactive Voice Response System (IVRS) used to randomize subjects. Otherwise, age will be calculated relative to the date of informed consent with the following formula:

(Date of informed consent - date of birth) 365.25.

Age in years and months obtained from the IVRS will be used to derive separately, age in months (integer) and age in years (2 decimal places), as follows:

Age (months) = IVRS age (months) + (IVRS age [years] \times 12)

Age (years) = IVRS age (years) + (IVRS age [months] / 12)

The age at first diagnosis will be given in years and will be derived applying all rules for missing date imputation (see Section 4.2.5) with the following formula:

(Date of first diagnosis of epilepsy – date of birth) / 365.25.

Epilepsy duration (years) will be calculated as:

(Date of informed consent – date of first diagnosis of epilepsy) / 365.25.

Age group categories are as reported in the eCRF and are as follows:

- ≥ 1 to ≤ 6 months
- \geq 6 months to <1 year
- ≥ 1 to ≤ 2 years
- ≥ 2 to ≤ 4 years

3.2.8 Body Mass Index (BMI)

BMI will be calculated as follows using height and weight at Visit 1; if weight is missing at Visit 1 then weight at Visit 2 will be used:

 $BMI = weight (kg) / (height [m])^2$

3.2.9 Electrographic partial-onset seizures

Electrographic seizures are defined as recognizable ictal patterns on an EEG involving ≥ 2 contiguous electrodes. The seizures are initiated as a unilateral or strongly asymmetric abnormal epileptiform discharge lasting a total of > 10 seconds.

The video-EEG recordings will be evaluated locally by the investigator, sub investigator, or qualified designated reader. Subjects who discontinue on or before Day 20 will not require an End-of-Maintenance Period video-EEG.

For the purposes of this SAP, the term electrographic partial-onset seizures will be used to define electrographic partial-onset seizures with or without clinical correlate; electrographic and electroclinical partial-onset seizures will be included for subjects aged ≥1 month to ≤6 months, and electroclinical partial-onset seizures will be included for subjects aged >6 months to <4 years.

Infants aged ≥ 1 month to ≤ 6 months

Partial-onset seizure frequency for infants aged ≥1 month to ≤6 months will be based on electrographic seizures.

The total number of partial-onset seizures is calculated as the total number of type IA/IB electrographic seizures plus the total number of type IA/IB electroclinical seizures plus the total number of type IC seizures.

The total number of seizures is calculated as the total number of partial-onset seizures (as defined above) plus the total number of other seizure types reported.

Infants aged >6 months to <4 years

Partial-onset seizure frequency for infants aged >6 months to <4 years will be based on electrographic seizures with an accompanying clinical correlate.

The total number of partial-onset seizures is calculated as the total number of type IA/IB electroclinical seizures plus the total number of type IC seizures.

The total number of seizures is calculated as the total number of partial onset seizures (as defined above) plus the total number of other seizure types reported.

Calculation of the End-of-Baseline Period ADF of electrographic partial-onset seizures will be based on the results from a video-EEG (up to 72 hours of continuous recording with every attempt to obtain at least 48 hours of interpretable recording) at Visits 2 and 3. The End-of-Maintenance Period ADF of electrographic partial-onset seizures will be based on results from a video-EEG (up to 72 hours of continuous recording with every attempt to obtain at least 48 hours of interpretable recording) at Visit 6.

3.2.10 ADF of Electrographic partial-onset seizures

The ADF of electrographic partial-onset seizures will be calculated as (number of partial-onset seizures as recorded on the video-EEG divided by the number of interpretable hours recorded)

of electrographic partial-onset seizures

The change in ADF of electrographic partial-onset seizures is calculated as the ADF of electrographic partial-onset seizures from the End-of-Maintenance Period video-EEG minus the ADF of electrographic partial-onset seizures from the End-of-Baseline Period video-EEG

3.2.12 Percent change in ADF

The percent change in ADF

electrographic partial-onset seizures from the End-of-Maintenance Period video-EEG minus the ADF of electrographic partial-onset seizures from the End-of-Baseline Period video-EEG divided by the ADF of electrographic partial-onset seizures from the End-of-Baseline Period video-EEG and then multiplied by 100.

3.2.13 Percent reduction in ADF of electrographic partial-onset seizures

The percent reduction in ADF of electrographic partial-onset seizures is calculated as the ADF of electrographic partial-onset seizures from the End-of-Baseline Period video-EEG minus the ADF of electrographic partial-onset seizures from the End-of-Maintenance Period video-EEG divided by the ADF of electrographic partial-onset seizures from the End-of-Baseline Period video-EEG and then multiplied by 100.

3.2.14 Response to treatment

Response to treatment is based on the percent reduction in ADF of electrographic partial-onset seizures. Subjects who experience 50% or greater reduction in their electrographic partial-onset seizures recorded on the End-of-Maintenance Period video-EEG compared to the End-of-Baseline video-EEG will be considered a responder.

3.2.15 Seizure-free status

At least 48 hours of interpretable recordings during the End-of-Maintenance Period video-EEG is required to determine a subject's seizure-free status. As above, the term electrographic partialonset seizures will be used to define electrographic partial-onset seizures with or without clinical correlate; electrographic and electroclinical partial-onset seizures will be included for subjects aged ≥ 1 month to ≤ 6 months, and electroclinical partial-onset seizures will be included for subjects aged >6 months to <4 years

All seizures

A subject is considered seizure free from all seizures if the End-of-Maintenance Period video-EEG has 0 (zero) seizures reported, that is, from all seizure types not just partial-onset seizure types.

Partial-onset seizures

A subject is considered seizure free from partial-onset seizures if the End-of-Maintenance Period video-EEG has 0 (zero) partial-onset seizures reported.

Confidential Page 18 of 93

Pediatric Quality of Life inventory (PedsQL) 3.2.16

Physical Functioning

• Cognitive Functioning

• Cognitive Functioning

• Physical Functioning

• Physical Functioning

• Physical Functioning

• Physical Functioning

• Cognitive Functioning

• Physical Functioning

• Physical Functioning

• Cognitive Functioning

• Physical Functioning

• Cognitive Functioning

• Cognitive Functioning

• Physical Functioning

• Cognitive Functioning

• Physical Functioning

• Physical Functioning

• Physical Functioning

• Physical Functioning The PedsQL is a validated instrument that consists of generic core scales suitable for use of

Physical Functioning
Emotional Functioning
Social Functioning
School Functioning

The PedsQL assessment is retrospective to the prior one month, and individual items are scored using a 5-point Likert scale (0 to 4 representing responses of: never, almost never, sometimes, often, or almost always). These scores of 0 to 4 will be transformed by the function: 100 – (response x 25) in order to generate scores of 0, 25, 50, 75, and 100 where a higher value represents a better health-related quality of life (HRQoL).

Each scale score is then calculated as the mean of the non-missing categorized items if 50% or more of the items are non-missing.

The above algorithm will also be used to calculate an overall total scale score (all scales), the psychosocial health summary score (a combination of the emotional, social, and cognitive functioning questions), and the physical health summary score (a combination of the physical functioning and physical symptoms questions) for each subject \(\leq 24 \) months of age, and an mountail, social, and school functioning questions), and the physical functioning questions) for each subject >2 years age.

4 STATISTICAL/ANALYTICAL ISSUES

4.1 Adjustments for covariates

ions of variations thereof. The primary efficacy analysis and planned sensitivity analyses will be adjusted for logtransformed Baseline seizure ADF, age category (4 age stratification categories, pooled as appropriate) and center (appropriately pooled) in the analysis of covariance (ANCOVA) models. Other statistical models may be adjusted for covariates, and any such adjustments will be described in the context of the analyses performed.

4.2 Handling of dropouts or missing data

4.2.1 Missing data

No imputation of missing values for analysis parameters is planned unless otherwise noted. Imputations for missing or partial values for dates for AEs and medications will be applied to determine if an event is to be considered treatment-emergent or concomitant, respectively. Across safety and efficacy analysis, only reported data will be used in each analysis time interval.

With respect to AEs, events with missing intensity will be assumed to be severe. Events with missing relationship to treatment per the investigator will be assumed to be related. It is not expected that events will have missing seriousness, but if they do, seriousness will not be imputed and will be left as missing. Incomplete or missing dates for events will be handled as described in Section 4.2.2.

Incomplete dates for adverse events and concomitant medications 4.2.2

For analyses of AEs and concomitant medication usage, a complete date must be established in order to correctly identify the AE or medication as occurring during treatment or not. For purposes of imputing missing components of partially-reported start and stop dates for AEs and for medication use, the algorithms listed below will be followed. Start and stop dates of AEs or medications will be displayed as reported in the subject data listings (ie, no imputed values will be displayed in data listings).

- Missing start day, but month and year present: If the start of treatment occurred in the same month and year as the occurrence of the AE/medication, the start day of the event/medication will be assigned to the day of first dose of study medication. Otherwise the start day will be set to the 1st day of the month.
- Missing start day and month, but year present:
- If the start of treatment occurred in the same year as the occurrence of the ÀE/medication, the start day and month will be assigned to the date of first dose of study medication. Otherwise the start day and month will be set to January 1st.
- Missing end day, but month and year present: The end day will be set to the last day of the month.
- Missing end day and month, but year present:

The end day and month will be set to the maximum of the date of study termination or the date equivalent to 30 days after last dose of study medication.

However, if the study termination year and year for the date which is 30 days after last dose of

Definition of concomitant medication in case of missing dates

With respect to definition of medication as concomitant, the following rule will be applied in case of completely missing stop and/or start date information:

Medications with a missing start date whose stop date is either first dose of study medication. Will be medication. medication. Medications with a missing start date whose stop date is prior to the date of first dose of study medication will be considered as prior medication, but not as concomitant medication. Medications with a missing stop date and a start date prior to the data of last dose of study medication will be considered as concomitant medication.

In subject data listings, dates will be displayed as reported.

Incomplete dates for the last administration of study medication 4.2.4

For purposes of imputing missing components of partially reported dates for the last administration of study medication, the algorithms listed below will be followed. Stop dates of study medication will be displayed as reported in the subject data listings (ie, no imputed values will be displayed in data listings).

- Missing last administration day, but month and year present: The last administration day will be set to the last day of the month or the date of the final contact, whichever is earlier in the month.
- Missing last administration day and month, but year present: The last administration day will be set to the last day of the year or the date of the final contact, whichever is earlier in the year.
- Completely missing date of last administration:

For calculating the duration of exposure, if the date of last administration is completely missing and no information could be obtained from data cleaning exercises, the date of last administration should be imputed as the date of last contact according to the Study Termination eCRF module. For all other purposes, no imputation will be done if the date of last administration is completely missing.

If a subject died during the study, and the imputed last administration date according to the rules above is after the date of death, the last administration date will be assigned to the date of death.

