6 SELECTION AND WITHDRAWAL OF SUBJECTS

6.1 Inclusion criteria

To be eligible to participate in this study, all of the following criteria must be met:

1. An Institutional Review Board (IRB)/Independent Ethics Committee (IEC) approved written Informed Consent form is signed and dated by the parent(s) or legal representative(s)/caregiver(s) (in accordance with local regulation).
2. Subject's parent(s) or legal representative(s)/caregiver(s) is considered reliable and capable of adhering to the protocol visit schedule or medication intake according to the judgment of the investigator.
3. Subject is male or female from ≥ 1 month (ie, 4 weeks after full term [37 weeks gestational age]) to < 4 years of age. For preterm infants < 1 year old, the corrected gestational age should be used when determining eligibility. The generally accepted definition of corrected gestational age, which is calculated by subtracting the number of weeks born before 37 weeks of gestation from the chronological age, will be used for this study.
4. Subject has a diagnosis of epilepsy with partial-onset seizures. The results of ≥ 1 prior EEG and ≥ 1 magnetic resonance imaging/computerized tomography scan should be consistent with this diagnosis.
5. Subject weighs ≥ 4 kg to < 30 kg at Visit 1.
7. Subject has experienced ≥ 2 partial-onset seizures with or without secondary generalization during each consecutive 7-day period during the 2 weeks prior to Visit 1.
- 8a. Subject has ≥ 2 partial-onset seizures with or without secondary generalization during the End-of-Baseline video-EEG. Electrographic seizures are defined as recognizable ictal patterns on an EEG involving ≥ 2 contiguous electrodes. The seizures are initiated as a unilateral or strongly asymmetric abnormal epileptiform discharge lasting a total of > 10 seconds.
9. Subject is on a stable (concurrently or sequentially) dosage regimen of 1 to 3 AEDs. The dosage regimen of concomitant AED therapy must be kept constant for a period of ≥ 2 weeks prior to Visit 1. A stable daily dosage regimen of a concomitant benzodiazepine (BZD) will be considered as a concomitant AED.
10. Vagus nerve stimulation is allowed and will not be counted as a concomitant AED. The VNS device must have been implanted for ≥ 6 months prior to Visit 1; device settings must be kept stable for ≥ 2 weeks prior to Visit 1 and kept stable during the Baseline, Treatment, and Transition Periods. Use of the VNS device magnet is allowed.

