11 ASSESSMENT OF SAFETY

11.1 Adverse events

11.1.1 Definition of adverse event

An AE is any untoward medical occurrence in a patient or clinical investigation subject administered a pharmaceutical product that does not necessarily have a causal relationship with this treatment. An AE can therefore be any unfavorable and unintended sign (including an abnormal laboratory finding), symptom, or disease temporally associated with the use of a medicinal (investigational) product, whether or not related to the medicinal (investigational) product.

In order to ensure complete safety data collection, all AEs occurring during the study (ie, after the signing of the Informed Consent form), including any pretreatment and posttreatment periods required by the protocol, must be reported in the eCRF even if no investigational product was taken but specific study procedures were conducted. This includes all AEs not present prior to the initial visit and all AEs that recurred or worsened after the initial visit.

Signs or symptoms of the condition/disease for which the investigational product is being studied should be recorded as AEs only if their nature changes considerably or their frequency or

intensity increases in a clinically significant manner as compared to the clinical profile known to the investigator from the subject's history or the Baseline Period.

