The number of previous AEDs defined as AEDs taken and stopped >14 days prior to Visit 1 (ie, prior to entry into the Baseline Period), and not taken during the course of the study, will be summarized by treatment group and overall for the SS based on the following categorization: 0 AEDS, 1 to 3 AEDs, 4 to 6 AEDs, and \geq 7 AEDs.

AEDs taken prior to the Baseline Period 6.4.2

The number and percentage of subjects taking AEDs prior to the Baseline Period defined as iations thereof AEDs with a start date prior to the date of informed consent, ie, prior to entry to the Baseline Period, excluding previous AEDs, will be summarized by WHODD chemical subgroup (Level 4) and preferred drug name, and by treatment group and overall for the SS.

6.4.3 **AEDs taken during the Baseline Period**

The number and percentage of subjects taking AEDs during the Baseline Period defined as AEDs with a start date on or after the date of informed consent and prior to the first dose of study medication, and AEDs with a start date prior to the date of informed consent and with a stop date on or after the start of the Baseline Period, will be summarized by WHODD chemical subgroup (Level 4) and preferred drug name, and by treatment group and overall for the SS.

AEDs taken on day of first dose of study medication 6.4.4

The number and percentage of subjects taking AEDs on the day of first dose of study medication, excluding AEDs taken as rescue medication, will be summarized by treatment group and overall for the SS based on the following categorization: 1 AED, 2 AEDs, and 3 AEDs.

The number and percentage of subjects taking AEDs on the day of first dose of study medication, excluding AEDs taken as rescue medication, will be summarized by WHODD chemical subgroup (Level 4) and preferred drug name, and by treatment group and overall for the SS.

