10.2 Adverse events

Adverse events will be tabulated by MedDRA system organ class (SOC) and MedDRA preferred term (PT). The number and percentage of subjects experiencing each event at least once will be summarized. All summaries will be sorted alphabetically by SOC and by frequency of events within PTs, starting with the most frequent event overall.

Adverse events will be classified as pre-treatment, treatment-emergent, or post-treatment. Pretreatment AEs are defined as AEs which had an onset date prior to the first dose of study medication.

Treatment-emergent AEs (TEAEs) will be defined as those events that start on or after the date of first study medication administration and within 30 days following the date of final study medication administration, or whose severity worsens within this time frame.

Post-treatment AEs are defined as AEs which had an onset date more than 30 days after the last dose of study medication.

All AEs reported during the study including pre-treatment and post-treatment AEs will be provided in a subject data listing.

An overall summary of AEs during the Treatment Period will provide the overall summary of TEAEs and the numbers and percentages of subjects with at least 1 TEAE, with a serious TEAE, with a drug-related TEAE, with a severe TEAE, and with a drug-related serious TEAE. The number and percentage of subject discontinuations due to TEAEs, and the number and percentage of subjects with AEs leading to death and with TEAEs leading to death (if applicable), during the Treatment Period, will also be summarized. The overall summary of AEs during the Treatment Period will be repeated by treatment group and age group using the levels defined in Section 3.2.7.

In addition, an overall summary of AEs during the Titration, Maintenance, Transition, Taper, and Safety Follow-Up Periods, and overall, separately, will be presented for each treatment group.

The following summaries of AEs will be provided for each treatment group by MedDRA primary SOC and PT:

- Incidence of TEAEs during the Treatment Period
- Incidence of serious TEAEs during the Treatment Period
- Incidence of TEAEs leading to discontinuation of study medication during the Treatment Period

 ee of these summaries will then be repeated by treatment group and age group was defined in Section 3.2.7.

All three of these summaries will then be repeated by treatment group and age group using the levels defined in Section 3.2.7.

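### The SAP's partial-date rule can set an AE or medication start to first dose even when a known stop date or a pre-treatment record shows that it began earlier

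*SAP*

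**What the plan says.** SAP 4.2.1 gives the purpose of imputing partial AE and medication dates: the imputations "will be applied to determine if an event is to be considered treatment-emergent or concomitant". SAP 4.2.2 then sets the start rules.

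- Day missing, month and year equal to those of treatment start: "the start day of the event/medication will be assigned to the day of first dose of study medication".
- Day and month missing, year equal to that of treatment start: "the start day and month will be assigned to the date of first dose of study" medication.
- Year only, any other year: "Otherwise the start day and month will be set to January 1st". With the day missing and any other month, the start becomes the 1st of that month.

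The classifications downstream depend on the start date. SAP 10.2 defines TEAEs as "those events that start on or after the date of first study medication administration" and up to 30 days after the last dose, or events that worsen in that time. SAP 6.4 assigns medications to study periods by start date. SAP 6.4.2 covers "AEDs with a start date prior to the date of informed consent, ie, prior to entry to the Baseline" Period, leaving out previous AEDs. SAP 6.4.3 needs a start between consent and first dose, or a start before consent with a stop on or after the beginning of Baseline. SAP 6.4.6 and 6.4.7 use the same start-date logic for non-AEDs.

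Two protocol provisions bear on this. Section 11.1.1 collects "all AEs occurring during the study (ie, after the signing of the Informed Consent form), including any pretreatment and posttreatment periods". Inclusion criterion 9 in section 6.1 says "The dosage regimen of concomitant AED therapy must be kept constant for a period of" at least 2 weeks before Visit 1.

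**The concern.** Defaulting to first dose is a sensible, cautious choice when the timing of an AE is really unknown. It is wrong when other data on the same record settle the matter. A stop date before Day 1 proves that an AE is pre-treatment. A record of an AED as ongoing at Visit 1 proves that it did not begin on Day 1. The start rules look at neither.

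At stake are the internal consistency of the TEAE counts and the description of background therapy. The same child's AED would appear in the tables of AEDs on the first-dose day (6.4.4) and concomitant AEDs (6.4.5) but be missing from the Baseline AED table (6.4.3). An AE could carry a start later than its own stop.

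**Working it through.** The plan gives no figure to reproduce, so the check applies the rule to worked cases.

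**Inputs.** The start rules (SAP 4.2.2), the TEAE definition (10.2), the medication table definitions (6.4.1 to 6.4.5) and criterion 9. The dates are invented for illustration: consent 13 Nov 2019, first dose 20 Nov 2019.

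| Record | Imputed start | Result |
|---|---|---|
| AE, start Nov 2019 or 2019, stop 17 Nov 2019 | 20 Nov 2019 | TEAE; start 3 days after stop |
| AED, start 2019, ongoing | 20 Nov 2019 | Titration Period; absent from 6.4.2 and 6.4.3; still in 6.4.4 and 6.4.5 |
| AED, start 2018, ongoing | 1 Jan 2018 | Correctly pre-treatment |
| AED, start Feb 2019, ongoing | 1 Feb 2019 | Correctly pre-treatment |

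The second row contradicts criterion 9. Two weeks of stable dosing before Visit 1 (Day -7) puts a qualifying background AED nominally at least 14 + 7 = 21 days before first dose.

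**Does another rule rescue these records?** SAP 4.2.5 (earliest calendar date) expressly leaves out AE and concomitant-medication dates. The section on defining concomitant medication when dates are missing does compare the stop date with first dose, but only when a date is completely missing. A medication with no start date therefore has its stop date respected, while one with a known year does not.

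**How often would the rule act on a date that is already partial?** Assume first doses are spread evenly over a 365-day year, and let L be the true number of days from start to first dose.

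- Year-only date: the chance of a match is (365 - L)/365. For L = 21 this is 344/365 = 94%; for 90, 275/365 = 75%; for 180, 185/365 = 51%; for 300, 65/365 = 18%; for 365 or more, 0%.
- Month-and-year date, L up to 28: each month loses L of its days, so the chance is (365 - 12L)/365. For L = 21 this is 113/365 = 31%.
- AE starts spread evenly over a 7-day Baseline (mean L = 4): (365 - 48)/365 = 87%. Over a 14-day Baseline, which the protocol permits (mean L = 7.5): (365 - 90)/365 = 75%.

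These are chances given a partial date. The documents do not give the share of dates that are partial, so they cannot be turned into a count of affected records.

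**The case against.** The strongest reply is that the stated purpose of the imputation is to settle treatment-emergent and concomitant status, and that an ongoing AED moved to Day 1 is still, correctly, concomitant. This stands as far as it goes. The AED also stays in the first-dose-day tables by count and drug name, so much of the description of background therapy survives. Listings show dates as reported. But if 4.2.2 is not meant for the period tables in 6.4, no rule covers them, because 4.2.5 excludes these dates. Either reading needs a sentence.

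For AEs, the reply is that few can be affected. The event must fall in a 7- to 14-day window and have a known stop but an unknown start day, despite AE reporting at Visits 1, 2 and 3. Such events precede treatment, so the error is balanced between arms in expectation and leans toward over-reporting. That limits the size, but the stop date still contradicts the classification.

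In the copy reviewed, the end-date rule of 4.2.2 breaks off in mid-sentence. The start rules are intact, but a guard in the lost lines cannot be excluded.

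A reader might infer more than the documents support:

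- That long-standing AEDs in general become on-treatment starts. Only AEDs begun in the calendar year of first dose, so less than 12 months earlier, can be moved.
- That AEDs finished well before the trial are lost. If stopped more than 14 days before Visit 1 and not taken during the study, they belong to 6.4.1, are excluded from 6.4.2, and fall outside 6.4.3 whatever start is imputed.
- That children would be removed from the Per Protocol Set. The deviation criteria sit in a separate document, the list is agreed at blinded meetings, and nothing says that imputed medication dates feed it.

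**Conclusion.** The point holds in a limited form. As visible, SAP 4.2.2 imputes first dose on a calendar match alone and can contradict a known stop date or a documented pre-treatment record. The consequences are a small number of pre-treatment AEs counted as TEAEs, and omissions from the descriptive tables in 6.4.2, 6.4.3, 6.4.6 and 6.4.7.

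The number of affected records cannot be estimated from the documents; any count would rest on an assumed share of partial dates. Given a year-only date, the chance of misdating runs from 94% for an AED begun 21 days before first dose to zero at 365 days or more, if first doses are spread evenly over the year. Primary efficacy is unaffected, and no effect on the Per Protocol Set is shown. This is a minor correction, worth making because a stated rule yields a classification that the data on the same record disprove.

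**What to change.** Add a guard to SAP 4.2.2. Use the first-dose date for a partial start only if both conditions hold:

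1. the stop date is missing or falls on or after first dose; and
2. the record is not documented as present before first dose, for example as ongoing at Visit 1 or in the AED history.

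Otherwise impute the earliest date consistent with the partial date, no earlier than the birthdate and never after a known stop date. An AE that stopped before first dose then stays pre-treatment.

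The birthdate floor is needed because a plain earliest-date rule gives 1 January for a year-only start, which would precede the birth of an infant born later that year. SAP 4.2.5 already uses the birthdate this way for diagnosis dates. State also whether the imputed dates drive the period tables in 6.4.

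The cost is about two sentences and one derivation, settled before unblinding. No new data are needed.
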